Lymphadenectomy has different objectives: staging the tumor in the surgical act and trying to perform a complete resection to improve oncological results, this way evaluating the quality of the surgical procedure. There is a direct correlation between the number of lymph nodes excised, and therefore evaluated, with survival. For a long time is known that the existence of ganglia in the surgical piece depends on the surgical technique and the methodology used. The Clinical Guidelines recommend a minimum of 12 lymph nodes studied for a correct tumor stage. For years, minimally invasive surgery is performed in a large number of interventions in a safe way. Jacobs et al described the first laparoscopic resection in sigma cancer in 1991. Since then the experience has grown rapidly, and different clinical trials showed improvements in the postoperative period of the patient without oncological differences. Only the Lacy study showed greater lymph node excision with the laparoscopic technique.

At present laparoscopic surgery has show to be a safe technique, which a better recovery of the patient (decreasing postoperative ileus, early oral diet, more controlled pain, fewer days of hospital stay ...) and also reduces the rates of complications if performed by experienced surgical teams. The most recent randomized studies have shown no oncological differences with respect to open surgery. The percentage of conversion in the literature varies from 2 to 46% depending mainly on the experience of the team.

Among surgical techniques by means of minimally invasive surgery, right colectomy can be considered a particular case in which the technical difficulty added by the frequent anatomical variations, especially vascular ones, have meant a more gradual acceptance of the laparoscopic approach. Unlike the technique used in rectal-sigmoid neoplasms, ileocolic anastomoses after right hemicolectomy can be performed in two ways: extracorporeal or intracorporeal.

The extracorporeal anastomosis is performed by externalizing the ileum and colon through the incision through which the surgical specimen is extracted. The intracorporeal anastomosis is performed completely laparoscopically, and the incision made is only to remove the surgical specimen.

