## **JUSTIFICATION:**

Right hemicolectomy using a minimally invasive technique allows for an earlier recovery, with less postoperative pain and less hospital stay. After right hemicolectomy, the ileocolic anastomosis is not performed "naturally" as is habitually done in low anterior resections or sigmoidectomies. There is, therefore, no standardization in the reconstruction technique, with two possibilities: intracorporeal and extracorporeal anastomosis.

The intracorporeal anastomosis allows proper visualization of it, ensuring adequate conformation (absence of rotation or traction), in addition allowing the closure of the mesos and avoiding the possible appearance of internal hernia, also allowing to choose the location and length of the incision necessary for the extraction of the piece. On the other hand, it is a difficult technique that requires high training in advanced laparoscopy.

The extracorporeal anastomosis is performed by extracting both ends (terminal ileum and transverse colon) through the incision through which the piece is obtained, and the anastomosis is performed. It does not require, therefore, an important training in intracorporeal sutures. On the contrary, it forces to make the abdominal incision in the area that allows the extraction of said ends. In obese patients it can be difficult since the mesos are short and do not allow their extraction easily, so sometimes, it forces excessive traction. In addition, intestinal rotations during the anastomosis may go unnoticed.

Although there are currently defenders of both techniques, the extracorporeal anastomosis is currently the most performed in our environment and will be used as a reference treatment in the present study.

Numerous studies have been published comparing both techniques. A very recent meta-analysis, including 12 non-randomized comparative studies with 1492 patients, concluded that intracorporeal anastomosis is associated with less morbidity and a reduction in hospital stay, suggesting a faster recovery. To date, no well-designed, prospective, randomized and randomized study exists in the literature. We believe it is necessary, therefore, to carry out a project that compares both surgical techniques in the treatment of right colon cancer and assess which is associated with a lower postoperative morbidity.

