## **MATERIALS AND METHODS:**

Patients treated in 4 Spanish South-east hospitals with preoperative diagnosis of right colon neoplasm were included. All participating hospitals have vast experience in minimally invasive approach.

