### **Study Design**

The IVEA-study is a prospective multicenter randomized trial with two parallel groups being done IA or EA in laparoscopic right hemicolectomy for right colon neoplasia. The patients were randomized using <http://www.randomization.com>.

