### **Outcome Measures**

Patient baseline characteristics at the time of surgery; age, gender, ASA score, major comorbidities and operative variables were obtained from each patient. The 30-day postoperative complications were recorded. Complications were defined as any deviation from the normal postoperative course and graded using Clavien-Dindo classification. The term anastomotic leakage (AL) defines all conditions with clinical or radiologic anastomotic dehiscence, with or without the need of surgical revision. Wound infection was defined as spontaneous drainage of purulent material from the wound or from the surgeon's deliberate revision and a positive culture of drained serous fluid. The length of hospital stay (LOS), reinterventions, postoperative pain according to the visual analogical scale were also documented. For the subsequent analysis of the patient, the conversion to an extracorporeal anastomosis among the totally laparoscopic procedures or conversion to open surgery has not been included.

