**Postoperative Management**

After surgery, nasogastric tubes were not used, the urinary catheters were removed on postoperative day 1. Early mobilisation was practised and oral fluids administered early, switched to a diet after first passage of flatus. and endovenous hydrations were suspended. Criteria for discharge included pain control, absence of nausea and tolerance of a soft diet without restrictions and passage of gas and stool. All patients were followed-up for at 30 days.

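### As worded, the protocol removes converted patients from the analysis after randomisation, on one ground that can arise only in the intracorporeal arm

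*Protocol*

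**What the plan says.** Study Design describes a "prospective multicenter randomized trial with two parallel groups being done IA or EA". The Chronogram has patients randomised first, with the technique following from the group. The Background says that only the intracorporeal anastomosis is done entirely by laparoscopy.

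The last sentence of Outcome Measures begins "For the subsequent analysis of the patient, the conversion to an extracorporeal anastomosis" and states in full that "the conversion to an extracorporeal anastomosis among the totally laparoscopic procedures or conversion to open surgery has not been included".

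No other section qualifies this. The eligibility criteria do not deal with intraoperative conversion. Statistical Analyses compares the two groups without naming an analysis population. Nothing provides for intention to treat or returns converted patients to their assigned arm.

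On how often conversion might occur, the Background says only: "The percentage of conversion in the literature varies from 2 to 46% depending mainly on the experience of the team". Materials and Methods adds: "All participating hospitals have vast experience in minimally invasive approach".

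**The concern.** Two kinds of conversion are named. Conversion to open surgery can happen in either arm. Conversion from intracorporeal to extracorporeal anastomosis can happen only to patients assigned to intracorporeal. If both lead to exclusion, the rule differs between the arms by construction and acts on an event that follows randomisation and may be related to outcome.

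The working hypothesis concerns morbidity in patients assigned to one technique or the other. Dropping patients in whom a technique could not be completed answers a different question: morbidity when the technique succeeds. The exclusion would affect 30-day morbidity (primary) and also leak, surgical-site infection, surgical time, stay and pain. A reader could not separate a treatment effect from the effect of the exclusion.

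The direction is not given. The Justification says of the intracorporeal technique that "it is a difficult technique that requires high training in advanced laparoscopy", and of extracorporeal extraction that "In obese patients it can be difficult since the mesos are short and do not allow their extraction easily". Either arm could plausibly have more conversions.

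**Working it through.** The protocol has no figure of its own on conversion to reproduce, so this is an illustration of what the exclusion could do.

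**Inputs from the protocol (Sample Size Calculation).** Morbidity 30% extracorporeal and 11% intracorporeal; one-sided 5% level; 75 per arm, raised for 10% drop-out to 75/0.9 = 83.3, so 84 per arm and 168 in total. Statistical Analyses names a chi-square test. (The 75 does not follow from the stated inputs; that is a separate matter and is not used here.)

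**Assumptions.** All conversion rates and converter risks below are assumed.

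**Formula.** Let an arm have overall morbidity p, conversion share c and converter risk r. The analysed rate after exclusion is (p − c·r)/(1 − c), which is lower than p by c(r − p)/(1 − c). The false difference is this shift in the intracorporeal arm minus the shift in the extracorporeal arm.

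**No true difference.** p = 30% in both arms, 84 per arm, the same r in both arms. Open conversion occurs in both arms and technique conversion in the intracorporeal arm only. Example with 5% open, 10% technique and r = 60%:
- extracorporeal: (0.30 − 0.05×0.60)/0.95 = 28.4%
- intracorporeal: (0.30 − 0.15×0.60)/0.85 = 24.7%
- false difference: 3.7 points in favour of intracorporeal

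Rejection rates come from exact enumeration, with the number of converters per arm binomial and a pooled z-test on the rest (two-sided, this is the chi-square without continuity correction). With all patients kept they are 5.1% one-sided and 5.1% two-sided.

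| Open (both arms) + technique (intracorporeal) | Converter risk | False difference (points) | One-sided | Two-sided |
|---|---|---|---|---|
| 2% + 2% | 40 / 50 / 60% | 0.2 / 0.4 / 0.6 | 5.4 / 5.7 / 6.0% | 5.1 / 5.1 / 5.1% |
| 5% + 5% | 40 / 50 / 60% | 0.6 / 1.2 / 1.8 | 5.9 / 6.9 / 8.1% | 5.1 / 5.3 / 5.7% |
| 5% + 10% | 40 / 50 / 60% | 1.2 / 2.5 / 3.7 | 7.0 / 9.6 / 12.9% | 5.3 / 6.3 / 8.1% |

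**When there is no bias.**
- Converters carry the average 30% risk: both shifts are zero, and rejection is 5.0 to 5.1% one-sided and 5.1% two-sided.
- Conversion is equal in both arms and converter risk is also equal: at 10% and 60%, both analysed rates are (0.30 − 0.10×0.60)/0.90 = 26.7%, and rejection is 5.1% one-sided and 5.0% two-sided.

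**When it runs the other way.**
- Extracorporeal converts 10% and intracorporeal 5%, converter risk 40 to 60%: the false difference is 0.6 to 1.8 points against intracorporeal; one-sided rejection falls from 4.3% to 3.0%, and two-sided rises from 5.1% to 5.7%.
- Converters have below-average risk (15%) and only intracorporeal patients are removed: at 5% removed the rate is (0.30 − 0.05×0.15)/0.95 = 30.8%, or 0.8 points against; at 10% it is (0.30 − 0.10×0.15)/0.90 = 31.7%, or 1.7 points against.

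**The case against.** The strongest objection is to the reading. Grammatically it is the conversion, not the converted patient, that is left out, and the sentence closes a paragraph listing what was recorded. It may mean only that conversion was not an analysed variable. What would then remain is an unnamed analysis population, which a protocol may leave to the SAP. This reading is possible, but the opening words concern the analysis of the patient and favour exclusion. A sentence open to that reading needs rewording in either case.

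The second objection is to the size. Under the two-sided chi-square, seven of the nine scenarios in the table stay between 5.1% and 5.7%; only 10% technique conversion with converter risk of 50% or more exceeds 6%. The larger inflation belongs to the one-sided level. This stands, and the hospitals' stated experience may point to low conversion. The grid is illustrative: it stops at 15% total conversion, while the only documented range reaches 46%.

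Third, balanced conversion removes the bias only if converter risk is also equal across arms. This is correct. With 10% conversion in each arm but risks of 60% (intracorporeal) and 40% (extracorporeal), the analysed rates are 26.7% and (0.30 − 0.10×0.40)/0.90 = 28.9%, a false difference of 2.2 points. Likewise, more conversion in the extracorporeal arm reverses the bias only if converters have above-average risk. These qualifications widen the uncertainty; they do not remove the concern.

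**Conclusion.** The concern holds. On its natural reading, the protocol excludes randomised patients for a post-randomisation event, and one of the two grounds exists in only one arm. Nothing elsewhere in the protocol restores analysis by assigned arm.

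The size is not known. Within the assumed grid the false difference favours intracorporeal by 0.2 to 3.7 points; under other assumptions it is nil or has the opposite sign. The protocol gives nothing that would settle which applies.

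The point must be fixed because the sentence determines the population for the primary and all secondary comparisons, and no later analysis of the retained patients alone would fully restore the randomised comparison. Confidence is medium, because the sentence admits a second reading.

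**What to change.** Replace the last sentence of Outcome Measures with:

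> The primary analysis is by intention to treat: all randomised patients are analysed in the arm assigned, including those converted to extracorporeal anastomosis or to open surgery. Conversions are reported by arm. An analysis without converted patients is a per-protocol sensitivity analysis only.

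Apply this to the primary and all secondary outcomes. It also settles the wording if the sentence meant only that conversion is not an outcome. How patients without a 30-day outcome are handled (the planned 10% drop-out) is a separate matter that this sentence does not resolve.

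**Cost.** One sentence. Postoperative Management already states "All patients were followed-up for at 30 days", so no visits are added. The estimate may become less favourable to the intracorporeal technique.

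Power is unchanged if the planned 11% already covers converted patients. If instead intracorporeal converters carry the 30% control rate (an assumption), that arm's rate becomes 0.11(1 − c) + 0.30c, i.e. 11.95%, 12.90% and 13.85% at 5%, 10% and 15% conversion. By the normal approximation with pooled null variance:

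| Analysed per arm | Conversion | One-sided power | Two-sided power |
|---|---|---|---|
| 84 | 5 / 10 / 15% | 89.6 / 86.0 / 81.7% | 82.6 / 77.5 / 71.9% |
| 75 | 5 / 10 / 15% | 86.4 / 82.3 / 77.6% | 78.1 / 72.7 / 67.0% |

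At the stated one-sided level, no extra patients are needed up to about 15% conversion with 84 analysed per arm, or about 10% with 75. If the test is two-sided, 80% power at 10% conversion needs 90 analysed per arm; with 10% drop-out that is 90/0.9 = 100 randomised per arm, 200 in total against the planned 168.

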### **Surgical technique**

Perioperative care was identical for both groups. Bowel preparation was not used, and intravenous antibiotics were administered preoperatively. Under general anesthesia, the patients were placed supine on the operating table, with open legs. Urinary catheter was inserted. Pneumoperitoneum was induced using carbon dioxide insufflated to an average pressure of 12 mmHg by placement of a infraumbilical trocar. Three additional ports were inserted: 12 mm in the left lower quadrant and two 5-mm trocars in the right lower quadrant and upper left quadrant. Laparoscopic right colectomy was performed with a medial-to-lateral approach, starting with ligation of the blood vessels at their origin followed by mobilization of the bowel and lateral

dissection of the terminal ileum and colon attachments. The colon and ileum were transected with a 60-mm laparoscopic stapler in that order, followed by an ileo-transverse anastomosis.

• **Intracorporeal anastomosis:**

The specimen was preferentially extracted via a small Pfannenstiel-type incision with the protection of an Alexis Wound Protector (Applied Medical, Rancho Santa Margarita, California, USA). The incision for the extraction of the right colon is sutured in two layers by absorbable suture. The ileum was held by the assistant to prevent rotation of its mesentery. A stay suture was applied 10 cm proximal and distal to the stapled ends of the terminal ileum and colon, respectively, and then held by the assistant. An enterotomy and colotomy were made sharply at the antimesenteric corner of the staple lines. An isoperistaltic side-to-side anastomosis was fashioned with a 60-mm laparoscopic stapler. A 2-0 double-barbed suture was used to close the enterocolotomy, in two planes (the first submucosal, and the second sero-serous). The mesenteric defect and the mesocolon after the construction of either type of anastomosis were not closed. Drains were not used routinely.

• **Extracorporeal anastomosis**

The mobilized colon was externalized preferentially via a transverse or midline incision with the protection of an Alexis Wound Protector (Applied Medical, Rancho Santa Margarita, California, USA). A stay suture was applied 10 cm proximal and distal to the stapled ends of the terminal ileum and colon. An enterotomy and colotomy were made sharply at the antimesenteric corner of the staple lines. An isoperistaltic side-to-side anastomosis was fashioned with a 60-mm laparoscopic stapler. A 2-0 double-barbed suture was used to close the enterocolotomy, in two planes (the first submucosal, and the second sero-serous). The mesenteric defect and the mesocolon after the construction of either type of anastomosis were not closed. The incision for the extraction of the right colon and the realization of the anastomosis is sutured in two layers by absorbable suture. Drains were not used routinely.

**Postoperative Management**

After surgery, nasogastric tubes were not used, the urinary catheters were removed on postoperative day 1. Early mobilisation was practised and oral fluids administered early, switched to a diet after first passage of flatus. and endovenous hydrations were suspended. Criteria for discharge included pain control, absence of nausea and tolerance of a soft diet without restrictions and passage of gas and stool. All patients were followed-up for at 30 days.

**Ethics**

The study was presented to the Hospital Ethical Board and accepted as a multicenter randomized trial. The research was conducted conformed to the Helsinki Declaration and to local legislation. Patients gave informed consent to participate in the study. This study has been registered in XXXXX register with the number XXXXX.

**Sample Size Calculation**

The hypothesis of this trial is that IRA will reduce overall postoperative 30-day morbidity rate. The sample size calculation is based on the detection of significant difference in the primary endpoint parameter of the trial. We assumed a postoperative complication rate of 30% in ERA according with several complication rates after colorectal surgery. With an expected complication rate of 11% in IRA, the sample size necessary for the trial with a power of 80% and one-sided significance level of 0.05 was calculated to be 75 patients per group. An assumed 10% drop-out rate in this trial will raise the sample size to 84 patients per group. Therefore, at least a total of 168 patients have to be included to the trial.

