**Statistical Analyses**

Statistical analyses of any differences between the 2 groups were performed using SPSS version 22 (SPSS Inc. Chicago, IL). Data were presented as means  $\pm$  standard deviations or as medians and interquartile ranges where appropriate. For dichotomous outcomes, treatment groups were compared by means of the  $\chi^2$  test. The Mann–Whitney U test and Kruskal–Wallis tests were used for continuous, not normally distributed outcomes. For continuous normally distributed data, the ANOVA test was used.

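### The stated inputs (30% vs 11%, 80% power, one-sided 0.05) give 53 to 66 patients per group, not 75; with 75 the power is about 90%

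*Protocol*

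**What the plan says.** All the inputs are in the protocol's Sample Size Calculation. For the extracorporeal arm: "We assumed a postoperative complication rate of 30% in ERA". For the intracorporeal arm: "With an expected complication rate of 11% in IRA". The error rates and the result come in one clause: "with a power of 80% and one-sided significance level of 0.05 was calculated to be 75 patients per group". A 10% drop-out allowance then raises this to 84 per group, and the section concludes that "at least a total of 168 patients have to be included to the trial". No formula, software or continuity correction is named.

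Under Statistical Analyses, binary outcomes are assigned to the chi-square test ("For dichotomous outcomes, treatment groups were compared by means of the" χ² test). Neither its sidedness nor any correction is given there.

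**The concern.** The section gives everything needed to repeat the calculation, and repeating it yields a clearly smaller number. The gap is too large for rounding. Drop-out does not explain it either, because that allowance is added afterwards as a separate step.

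This section is the only justification for randomising 168 surgical patients. If its inputs and its result disagree, a reader cannot trace the target or know which of the stated assumptions actually produced it. The candidates have different consequences. A misstated power means that the trial is simply stronger than described. A misstated sidedness changes the significance level for which the trial was sized. A misstated event rate means that the protocol misreports its own target effect.

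**Working it through.** **Inputs (Protocol, Sample Size Calculation).** p1 = 0.30, p2 = 0.11, difference d = 0.19, equal groups, one-sided α = 0.05 (z = 1.645), power 80% (z = 0.842).

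**Quantities used below.** Mean rate = 0.205. 2 × 0.205 × 0.795 = 0.32595, square root 0.5709. 0.30 × 0.70 + 0.11 × 0.89 = 0.3079, square root 0.5549. d² = 0.0361.

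**Attempt to reproduce 75 per group on the stated inputs**

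- Pooled variance under the null: n = (1.645 × 0.5709 + 0.842 × 0.5549)² / 0.0361 = 1.406² / 0.0361 = 54.8, so 55.
- Unpooled variance: n = (1.645 + 0.842)² × 0.3079 / 0.0361 = 52.7, so 53.
- Pooled variance in both terms: n = (1.645 + 0.842)² × 0.32595 / 0.0361 = 55.8, so 56.
- Arcsine: h = 2·arcsin√0.30 − 2·arcsin√0.11 = 0.483; n = 2 × (1.645 + 0.842)² / h² = 53.0, so 53.
- Continuity-corrected: n′ = (n/4) × [1 + √(1 + 4/(n·d))]², giving 64.9 from the pooled n and 62.8 from the unpooled n, so 65 and 63.
- Simple additive correction: 54.8 + 2/0.19 = 65.3, so 66.
- Exact binomial enumeration: 80% is first reached at 53 per group for the uncorrected chi-square test (80.4%) and at 63 for one-sided Fisher (80.6%).

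The range is 53 to 66, so 75 is too high by 9 to 22 per group.

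**Drop-out step.** 75/0.9 = 83.3, rounded up to 84; 2 × 84 = 168. This is correct. The same step on the recomputed sizes:

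| Per group | After 10% drop-out | Total | Below 168 by |
|---|---|---|---|
| 53 | 59 | 118 | 50 |
| 55 | 62 | 124 | 44 |
| 63 | 70 | 140 | 28 |
| 65 | 73 | 146 | 22 |
| 66 | 74 | 148 | 20 |

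**Power of 75 per group at the stated rates.** Normal approximation, one-sided: Φ[(√75 × 0.19 − 1.645 × 0.5709) / 0.5549] = Φ(1.273) = 89.8%. For two-sided 0.05, 1.960 replaces 1.645: Φ(0.949) = 82.9%.

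| Method | One-sided 0.05 | Two-sided 0.05 |
|---|---|---|
| Normal approximation | 89.8% | 82.9% |
| Exact, uncorrected chi-square | 90.6% | 84.1% |
| Exact, Fisher | 86.8% | 78.4% |

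The Yates-corrected chi-square test gives the same figures as Fisher at 75 per group (86.8% and 78.4%).

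**Which changed input would give about 75?**

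- 90% power at one-sided 0.05: 73.0 (unpooled), 73.4 (arcsine), 75.4 (pooled).
- 85% power at one-sided 0.05 with continuity correction: 73.7 (pooled).
- An intracorporeal rate of about 13.4%, or an extracorporeal rate of about 26.8%, with everything else as stated: about 75 (pooled).
- Two-sided 0.05 at 80% power: 66.9 to 70.9 uncorrected and 77.1 to 79.9 corrected. These lie on either side of 75, but none equals it.

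Each near match needs a value other than the one printed.

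**The case against.** The strongest case on the other side accepts the arithmetic and disputes its weight. The error is on the safe side: under the chi-square test that the protocol names, 75 per group exceeds 80% power whether the level is one-sided (90.6%) or two-sided (84.1%). The correction changes no patient number, endpoint or analysis. The protocol states a one-sided level and a directional hypothesis, so the figure of about 78% power needs two departures from the text at once: a two-sided level, and a Fisher or Yates test. The alternative inputs are back-solved and nothing in the document supports them. The sidedness and correction of the primary test may be set out in a statistical analysis plan. And if the group size itself could be the error, advice to keep it seems to prejudge the answer.

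Much of this limits the point without removing it. No underpowering on the stated assumptions is claimed. The back-solved inputs are only possibilities, and the two-sided figures show only why the sidedness needs confirming. The silence under Statistical Analyses is context, not the fault. What remains is that the section prints its inputs and its result and the two conflict; a later plan cannot make that statement true. Keeping 75 is also consistent with the group size having been the misstated element. The stated rates and level then stand, and the power that 75 delivers is about 90%.

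**Conclusion.** The point holds. On the protocol's own inputs the required size is 53 to 56 per group uncorrected, or 63 to 66 with continuity correction or Fisher, against the stated 75. The total after drop-out would be 118 to 148 rather than 168. At the stated rates and one-sided level, 75 evaluable patients per group give about 90% power with the uncorrected chi-square test (86.8% with Fisher or Yates), not 80%.

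This rests on equal allocation, independent binomial outcomes and the stated rates. Within the standard methods, the choice of formula does not affect the conclusion. Which element was misstated cannot be determined from the protocol. The error should be corrected because the justification of the target is wrong as written, but it does not threaten the trial's power on its stated assumptions.

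**What to change.** Keep 75, 84 and 168. Retrieve the original calculation, name its formula and the test it assumes in Sample Size Calculation, and correct whichever element proves to be misstated:

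- If the rates and the one-sided 0.05 level stand, replace 80% by about 90% power (uncorrected chi-square).
- If the calculation was two-sided, state two-sided 0.05 with about 83% power for the uncorrected chi-square test, and give the same level for the primary comparison under Statistical Analyses.
- If an event rate was mistyped, correct it and restate the difference that the trial was sized to detect.

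The power should not be rewritten to fit the number before the original calculation has been checked. The cost is that check and a change of wording. Recruitment is unaffected.

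### The primary comparison is sized at one-sided 0.05, but the test named for it is a non-directional chi-square with no stated level or side, so the decision rule is not fixed

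*Protocol*

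**What the plan says.** The Sample Size Calculation section assumes complication rates of 30% (extracorporeal) and 11% (intracorporeal). The number needed "with a power of 80% and one-sided significance level of 0.05 was calculated to be 75 patients per group" is then raised to 84 per group, 168 in total, for 10% drop-out. No other significance level appears in the protocol.

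The Statistical Analyses section opens with "Statistical analyses of any differences between the 2 groups" and continues: "For dichotomous outcomes, treatment groups were compared by means of the" chi-square test. The primary endpoint, overall 30-day morbidity, is such an outcome. The section gives no level, no side and no statement on continuity correction.

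The purpose of the trial is worded in two ways. The Work Hypothesis and the first sentence of the Sample Size Calculation expect less morbidity with intracorporeal anastomosis, which is directional. The general objective is only to compare the techniques, and the Justification wants to "assess which is associated with a lower postoperative morbidity", which is open in both directions.

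**The concern.** The usual chi-square statistic for a 2×2 table squares the difference, so its p-value counts departures either way. Using it at one-sided 0.05 needs an added rule: check the sign and halve p, or equivalently require p below 0.10 with the difference in the expected direction. The protocol gives no such rule. A reader of the Statistical Analyses section alone would compare the printed p with 0.05, while a reader of the Sample Size Calculation would compare half of it with 0.05.

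The main claim of the trial could then depend on a choice made after the data are seen. The lenient choice doubles the chance of falsely declaring intracorporeal anastomosis superior. A one-sided rule also allows no conclusion that intracorporeal is worse, although the Justification asks which technique is better and describes intracorporeal as difficult and demanding of training.

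**Working it through.** **Inputs from the Sample Size Calculation:** p1 = 0.30, p2 = 0.11, difference d = 0.19, mean rate 0.205, power 80%, one-sided alpha 0.05, 75 per group (84 after drop-out).

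**1. The plan's own figure.** Pooled-variance formula:

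n = [zα·√(2·p̄·(1−p̄)) + zβ·√(p1(1−p1) + p2(1−p2))]² / d²

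Here √(2 × 0.205 × 0.795) = 0.5709, √(0.2100 + 0.0979) = 0.5549, d² = 0.0361 and zβ = 0.8416.

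- One-sided 0.05: (1.6449 × 0.5709 + 0.8416 × 0.5549)² / 0.0361 = 1.4061² / 0.0361 = 54.8, so 55 per group (65 with continuity correction).
- Two-sided 0.05: (1.9600 × 0.5709 + 0.8416 × 0.5549)² / 0.0361 = 1.5860² / 0.0361 = 69.7, so 70 per group (80 with continuity correction).

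The stated 75 is reproduced by neither. One-sided 0.05 gives 76 at 90% power, or 74 at 85% power with continuity correction, but both contradict the stated 80%. The drop-out step is right: 75 / 0.9 = 83.3, so 84 per group and 168 in total.

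**2. Power at the planned size.** By the same formula at 75 per group, two-sided 0.05: zβ = (0.19 × √75 − 1.9600 × 0.5709) / 0.5549 = (1.6454 − 1.1190) / 0.5549 = 0.949, which is 82.9%. Exact binomial enumeration at 30% v 11% gives:

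| Rule | 75 per group | 84 per group |
|---|---|---|
| One-sided 0.05, uncorrected | 90.6% | 93.2% |
| Two-sided 0.05, uncorrected | 84.1% | 88.1% |
| Two-sided 0.05, Yates-corrected | 78.4% | 83.2% |

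**3. A result on which the two readings differ.** Take 35 events in 150 patients: 22/75 (29.3%) extracorporeal v 13/75 (17.3%) intracorporeal. The pooled rate is 35/150 = 0.2333, the standard error is √(0.2333 × 0.7667 × 2/75) = 0.0691, and z = 0.12 / 0.0691 = 1.737. The chi-square p is 0.082 and the one-sided p is 0.041.

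**4. How often this happens.** Exact probability, at 75 per group with the uncorrected test, that the result favours intracorporeal with 1.645 < z ≤ 1.960:

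| Extracorporeal v intracorporeal | Probability |
|---|---|
| 30% v 11% (protocol) | 6.5% |
| 30% v 15% (assumed) | 11.9% |
| 30% v 18% (assumed) | 13.3% |
| 30% v 20% (assumed) | 12.4% |

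At 84 per group and 30% v 11% it is 5.1%.

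**5. False claims for intracorporeal.** With no true difference and 20.5% in both arms (an assumption, the midpoint of 30% and 11%), the rate is 5.0% at one-sided 0.05 and 2.5% at two-sided 0.05.

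**The case against.** A reader might infer that the protocol sets two thresholds, so that one result formally both succeeds and fails. The text does not support this. Only "one-sided significance level of 0.05" is written; two-sided 0.05 is how a chi-square p is conventionally read, and it appears nowhere in the document. The accurate statement is that the rule is not fixed.

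A reader might also infer that the research question is purely two-directional. It is not: the Work Hypothesis and the opening of the Sample Size Calculation are directional and fit a one-sided level. The document is mixed.

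Further points stand in part. A chi-square test can serve a one-sided level, because on a 2×2 table it is the square of the two-proportion z; but the rule that makes it do so has to be stated. The phrase about any differences introduces the analysis of all outcomes and is not a rule for the primary one. The discrepancy arises only for results favouring intracorporeal. The doubled false-positive rate is simply what one-sided 0.05 means, and the protocol declares that level openly. The 12–13% figures rest on intracorporeal rates that are not in the protocol. Keeping the sample size is free of cost only with an uncorrected test.

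Sidedness may be detailed in a statistical analysis plan not shown here, so silence in the Statistical Analyses section would not by itself be a finding. But the protocol itself fixes a one-sided level in one section and a non-directional test in another, and gives nothing to connect them.

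**Conclusion.** The point holds as a mismatch between the sizing level and the named test, within a document whose hypotheses are directional and whose aims are neutral. It leaves open how a result favouring intracorporeal with a chi-square p of 0.05–0.10 is to be judged. The chance of such a result is 6.5% under the protocol's own rates with 75 per group, and 12–13% if the true intracorporeal rate is 15–20%, which is an assumption. These figures assume 75 analysed per group, independent binomial outcomes and an uncorrected test.

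A two-sided 0.05 level is affordable at the planned size: 70 per group are needed for 80% power with the uncorrected test, against 75 planned. Separately, 75 does not follow from the stated one-sided 0.05 and 80% power.

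**What to change.** - **Sample Size Calculation:** state a two-sided 0.05 level. Keep 75 per group (84 after drop-out), and replace the present derivation with the power this size gives at 30% v 11%: about 83–84% at 75 per group with an uncorrected test. If a continuity correction is to be used, say so and give its power instead: 78% at 75 per group and 83% at 84 per group.
- **Statistical Analyses:** state that the primary comparison of 30-day morbidity is the uncorrected Pearson chi-square test at two-sided 0.05, with superiority claimed for whichever arm has the lower rate.

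The cost is a few sentences and no extra patients with the uncorrected test. With a continuity correction, 80 per group (89 after drop-out) would be needed for 80% power. The real downside is a stricter threshold for the hoped-for result: at 75 per group and 30% v 11%, exact power falls from 90.6% to 84.1%. In return, the false-superiority risk falls from 5.0% to 2.5%, and a conclusion in either direction becomes possible.
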